6.7 The 1.5 Prevention Criteria Testing

At the baseline visit, all subjects who have been identified as primary prevention indication subjects will be assessed to see if they further meet 1.5 Prevention Criteria; secondary prevention subjects do not need to undergo 1.5 Criteria testing. If one or more criteria are met, this subject will be classified as a 1.5 Subject. All criteria should be assessed, even if it is known that the subject already meets one of the four criteria. Patients should complete 1.5 testing prior to being asked if they want to have a device implanted.

The four criteria which will be assessed include:

- Pre-syncope/syncope
- Low left ventricular ejection fraction (low LVEF)
- Frequent premature ventricular contractions (PVCs)
- Non-sustained ventricular tachycardia (NSVT)

These criteria are described in Table 4 as well as below.

6.7.1 *Pre-syncope/Syncope*

History of recent pre-syncope/syncope will be collected from medical records, where recent is considered 12 months prior to subject enrollment (signing informed consent). In instances where no patient medical records are available, it is

36 © 1990 EuroQol Group EQ-5D™ is a trade mark of the EuroQol Group.

permissible for the investigator to rely on patient memory. This should be documented in the medical records.

In this study, a history of syncope classifies a subject as a 1.5 subject when the syncope is due to suspected VT. Unexplained syncope or pre-syncope will also classify a subject as a 1.5 subject, after ruling out vasovagal syncope, syncope related to bradycardia, and syncope related to supraventricular tachycardia (SVT).

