6.9.1 Implant Refusal

Subjects that choose not to receive a device implant will be asked the reason for refusal, which will be documented on the 'Implant/Implant Refusal' Case Report Form. Following refusal, primary indication subjects will be followed every 6 months until study closure or exit. These subjects will contribute to the study's secondary endpoint of mortality (see Section 12.3). Secondary indication subjects will exit the study upon refusal of implant.

With the exception of secondary prevention subjects, if a subject initially refuses implant, but later decides to receive an implant, a 'Device Change' CRF shall be completed (see Section 6.11).

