12.3.4 Determination of Patients/Data for Analysis

All subjects in the 1.5 prevention cohort at the time of enrollment will be included.

Version 1

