3.1.2 Special Considerations

Medtronic statisticians will perform the statistical analyses. Sample size estimates were calculated using SAS Version 9.2 (SAS Institute Inc.).

Analysis Cohort

Patients with any of the following deviations from the study protocol will be excluded from all statistical analysis, as if they were never enrolled in the study:

- Patients that violate any of the inclusion/exclusion criteria.

- Primary prevention patients that did not have LVEF measured at baseline or the 1.5 criteria assessment
- Patients with LVEF measured prior to 40 days post-MI OR prior to 90 days post-MI with revascularization.
- Primary ICD indication patient that is not Class I.
- Primary prevention patients without history of any 1.5 criteria and no Holter test performed
- Primary prevention patients without history of any 1.5 criteria and Holter test performed more than 12 months prior to enrollment or more than 3 months after enrollment.
- Primary prevention patients with no 1.5 criteria assessment.
- Patients with a Baseline or Medical History CRF dated after implant.
- Patients with consent date after implant decision date.
- Patients with previous ICD or CRT-D.
- Patients implanted with a Non-Medtronic device.
- Patients exiting the study or dying prior to completing the Medical History CRF, or the Implant CRF.

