Due to the large sample size, it is likely that some subjects will have covariates missing. To circumvent this problem, multiple imputation methods will be used. More specifically:

- The number of imputed datasets to be created will be 20.
- The imputation of missing values will be done using the fully conditional specification (FCS) method, where the covariates in the imputation model are the same covariates in the Cox proportional model (except the covariate being imputed) plus implant/no implant, the event indicator and the Nelson-Aalen estimator of the cumulative hazard function as suggested by White and Royston (2009).
- The imputation for missing binary variables (e.g., gender) will be done via the FCS logistic regression method, and for missing continuous variables (e.g., QRS) it will be done via the FCS linear regression method.
- Missing NYHA will be imputed via FCS ordinal logistic regression.
- All continuous variables will be standardized before the imputation phase, in order to avoid the FCS linear regression imputing values that are not realistic (e.g., negative LVEF).
- The null hypothesis will be rejected if the pooled p-value for the implant/no-implant covariate is less than 0.05.

The analysis will be performed using SAS code similar to:

```
/*Nelson-Aalen Estimates for Cumulative Hazard Function*/  
  
proc phreg data=alldataneeded1p5 noprint;  
  model SURVTIME*EVENT(0) =;  
  output out=alldataneeded1p5_2 logsurv=logs / method=emp;  
run;  
  
data Alldataneeded1p5_2;  
  set Alldataneeded1p5_2;  
  cumhaz = -logs;  
run;  
  
proc standard data = Alldataneeded1p5_2 mean = 0 std=1 out=  
Alldataneeded1p5_3;  
  var AGE LVEF0 QRS;  
run;  
  
/*Imputation Phase*/  
proc mi data= Alldataneeded1p5_3 n impute = 5 out = mi_alldata_1p5 ;  
class SEXCHAR CMYISCH LBBB NYHA0 DIABETES CRIT15SYNC CRIT15NSVT CRIT15PVC  
GROUP EVENT;  
var AGE SEXCHAR QRS CMYISCH LBBB NYHA0 DIABETES LVEF0 CRIT15SYNC CRIT15NSVT  
CRIT15PVC GROUP CUMHAZ EVENT;  
fcs logistic(SEXCHAR CMYISCH LBBB NYHA0 DIABETES CRIT15SYNC CRIT15NSVT  
CRIT15PVC GROUP EVENT);  
run;  
  
/*Analysis Phase*/  
proc phreg data = mi_alldata_1p5;  
class SEXCHAR CMYISCH LBBB NYHA0 DIABETES CRIT15SYNC CRIT15NSVT CRIT15PVC  
GROUP EVENT;
```

```

model SURVTIME*EVENT(0) = AGE SEXCHAR QRS CMYISCH LBBB NYHA0 DIABETES LVEF0
CRIT15SYNC CRIT15NSVT CRIT15PVC GROUP ;
by _Imputation_;
ods output ParameterEstimates=coxReg_fcs;
ods output Type3=type3table;
run;

/*Pooling Phase*/

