proc mianalyze parms(classvar=ClassVal) = coxReg_fcs;
class SEXCHAR CMYISCH LBBB NYHA0 DIABETES CRIT15SYNC CRIT15NSVT CRIT15PVC
GROUP;
modeleffects AGE SEXCHAR QRS CMYISCH LBBB NYHA0 DIABETES LVEF0 CRIT15SYNC
CRIT15NSVT CRIT15PVC GROUP ;
run;

```

Kaplan-Meier estimates of the survival curves will be displayed for each group.

The same analysis will be performed comparing implanted and not implanted 1.0 subjects.

Time to Event Considerations

- Time 0 is the enrollment date and subjects will be censored on the last date they were confirmed to be alive.
- Non-implanted patients that later decided to implant the ICD/CRT-D, will have their time to event censored at the day of the implant procedure.
- Implanted patients that explanted the device (without replacement) will continue to be followed as part of the implanted group. These cases will be rare, and unless the explant is completely voluntary (i.e., not due to infection, or imminent subject end-of-life), censoring subjects at explant would bias the results in favor of implant. This is an intention-to-treat approach.
- Patients that had heart transplant will have their time to event censored at the day of the transplant.

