3.3.2 Determination of Patients/Data for Analysis

All subjects in the 1.5 prevention cohort at the time of enrollment who do not meet the criteria in section 3.1.2 of this document will be included. The same criteria apply for the 1.0 subjects in their mortality analysis.

Hypothesis

Although this is an exploratory objective and is not powered, a hypothesis test will be done and compared to an alpha level of 0.05.

H_0 : Hazard ratio of patients with Chagas disease to patients without Chagas disease = 1
 H_a : Hazard ratio of patients with Chagas disease to patients without Chagas disease \neq 1

Only subjects with implant (regardless the prevention criteria group) will be included in the analysis. Subjects with missing information regarding Chagas disease will not be included.

The hypothesis will be tested separately for 1.0, 1.5, and secondary groups.

Analysis Methods

A Cox proportional hazard model will be used to compare the hazard rates of first appropriate VT/VF therapy between subjects with Chagas disease and subjects without Chagas disease within each group (1.0, 1.5, and secondary). The Cox proportional hazards model will only include the Chagas disease indicator. The null hypothesis will be rejected if the p-value for the Chagas disease indicator covariate is less than 0.05.

The analysis will be performed using SAS code similar to:

```
proc phreg data=alldataneeded ;
  class chagas;
  model firstVTVFappropTreat*event(0) = chagas;
run;
```

Time to Event Considerations

- Time 0 is the implant date and, if no events occur, subjects will be censored on the date of their latest device interrogation. Only spontaneous, appropriately treated VT/VF episodes as adjudicated by the episode review committee will count toward the endpoint.
- VT/VF episodes that cannot be adjudicated (due to not saving full episode data or any other reason) will be ignored. Often, these episodes are followed by episodes that can be adjudicated, and since the endpoint is time to first episode, effects on the results from these events will be minimal. In addition, these should be balanced between the comparison groups.

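### Mortality time starts at enrolment although subjects must survive to the implant or refusal record to be analysed; unequal delays would bias the hazard ratio slightly, and a delayed-entry term removes the bias

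*SAP*

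**What the plan says.** - SAP 3.3, Time to Event Considerations, sets the origin: "Time 0 is the enrollment date and subjects will be censored on the last date they were confirmed to be alive".
- SAP 3.1.2 lists subjects to be dropped from every analysis, including "Patients exiting the study or dying prior to completing the Medical History CRF, or the Implant CRF". SAP 3.3.2 carries this into the mortality cohort: 1.5 subjects "who do not meet the criteria in section 3.1.2 of this document will be included".
- Protocol 12.3.4 was wider: "All subjects in the 1.5 prevention cohort at the time of enrollment will be included". SAP 3.1.3 allows the SAP to override the protocol, so the narrowing itself is not the fault.
- The arm becomes known only after enrolment. Protocol 6.7 says "Patients should complete 1.5 testing prior to being asked if they want to have a device implanted", and Protocol 6.9.1 asks for the reason for refusal, "which will be documented on the 'Implant/Implant Refusal' Case Report Form". Implant and refusal thus share one form.
- The Cox model in SAP 3.3 begins "model SURVTIME*EVENT(0) = AGE SEXCHAR QRS CMYISCH LBBB NYHA0 DIABETES LVEF0" and ends with a fixed GROUP. It has no entry time and no time-dependent implant term.
- Subjects who first refuse and are implanted later are censored at implant. The same analysis is repeated in 1.0 subjects.

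**The concern.** The SAP changed who is analysed but left the clock where it was. Every analysed subject has, by definition, survived from consent to the implant or refusal record, and the model still counts that interval as follow-up during which a death could have been observed. This is guaranteed (immortal) time in both arms.

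If the interval has the same length in both arms, the hazard ratio is unaffected. If it differs, the arm with the later record gains extra death-free time. Implant records may well come later, because a procedure has to take place, but neither document says so.

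Nothing else in the plan corrects this. Censoring at late implant acts at the end of non-implanted follow-up, not at its start. Baseline covariates cannot adjust away guaranteed survival. Dropping the exclusion would not be enough either: with a fixed group, an implanted subject must still have lived to be implanted.

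At stake is a formal test at 0.05, to be read as a mortality difference by implant status.

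**Working it through.** Hazard ratios below are implanted/non-implanted; the SAP states the inverse.

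**Inputs.** Three-year mortality 25.7% without and 18.5% with an ICD, and 430 implanted vs 540 not (SAP 3.3.1). Accrual curve from the SAP Appendix simulation over 2.24 years plus 2 years of follow-up, with last contact 0–91 days before study end. Four-week visit cut-off, meant to let testing and implant or refusal data arrive for the last subjects enrolled (SAP 3.2, Sample Size Re-estimation). If both records fall inside it, the arms differ by at most 28 days: 28/30.44 = 0.92 month.

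**The plan's own figure.** For 450 vs 550 subjects and 18% vs 26% mortality, the tables give 88% power. HR = ln(0.82)/ln(0.74) = 0.659. Deaths = 450 × 0.18 + 550 × 0.26 = 224. By the Schoenfeld formula, √(224 × 0.45 × 0.55) × |ln 0.659| − 1.96 = 1.14, which is 87.4% power. The figure reproduces.

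**Hand check at 28 days vs 0, no true effect.** Hazard = −ln(1 − 0.257)/3 = 0.0990 per year. Implanted-arm deaths removed: 430 × (1 − exp(−0.0990 × 28/365.25)) = 430 × 0.00756 ≈ 3.25. In simulation 95.5 remain, so HR ≈ 95.5/(95.5 + 3.25) = 0.967.

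**Simulation under no effect.** Assumptions: constant hazard; testing uniform over 0–1 month in both arms; extra wait exponential with the stated mean (except the 28-day row); no other exits. HRs come from 20 million subjects (error about 0.001); rejection comes from 20,000 trials of 430/540 (error about 0.15 points).

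| Later record, by how much | HR, SAP method | Two-sided rejection |
|---|---|---|
| Equal delays | 1.001 | 5.0% |
| Implant, 0.25 month | 0.990 | 5.2% |
| Implant, 0.5 month | 0.982 | 4.9% |
| Implant, 0.92 month | 0.966 | 5.4% |
| Implant, exactly 28 days vs 0 | 0.967 | 5.7% |
| Refusal, 0.5 month | 1.017 | 5.2% |
| Refusal, 0.92 month | 1.034 | 5.7% |

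The SE of the log hazard ratio is about 0.138, so the bias is about 0.13 SE at 0.5 month and 0.25 SE at 0.92 month. Normal theory at 0.25 SE gives Φ(−1.71) + Φ(−2.21) = 5.7%. The false-benefit tail is 3.1%, 3.1% and 4.0% for implant later by 0.25, 0.5 and 0.92 month, against a nominal 2.5%.

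A separate numerical solution of the Cox score equation gave 0.968–0.969 with implant 28 days later, 1.032–1.034 with refusal 28 days later, and 1.000 with equal delays.

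**With the planning effect true.** HR = ln(1 − 0.185)/ln(1 − 0.257) = 0.689. With implant later by 0.92 month, the SAP method gives about 0.67 and p<0.05 in 78% of trials; delayed entry gives 0.69 and 70%.

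**Candidate corrections, no true effect.**
- Entry at the implant or refusal date: HR 0.999–1.001 in every scenario, rejection 4.8–5.2%, SE still 0.138.
- Entry at a decision date (end of testing): 0.990, 0.982 and 0.966 for implant later by 0.25, 0.5 and 0.92 month, so nothing is corrected.
- Falling hazard (Weibull shape 0.7, assumed; same three-year mortality; 0.92-month gap): SAP 0.934, time 0 reset to the record 0.959, delayed entry 0.999.
- 10% per year late implants unrelated to risk, censored as the SAP says, 0.92-month gap: SAP 0.964, delayed entry 0.999.

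**The case against.** The strongest reply is that the harm is conditional. No delay by arm is given, equal delays cause no bias, and the idea that implants are recorded later is inference. That stands: the plan permits a bias and does not demonstrate one.

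Second, the four weeks is a database-freeze rule, not a plan for or cap on time to implant. That also stands, so the size is less certain than the mechanism.

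Third, the exponential scenarios overrun the window: at the 0.92-month mean, about 66% of implant records fall after day 28. This is correct, but the exact 28-day case, which stays inside, gives the same hazard ratio. That case is itself an extreme. If testing takes 0–14 days, refusal follows at once and implants spread evenly to day 28, the ratio is about 0.986.

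Fourth, the small differences in rejection rate are largely simulation noise; normal theory puts the excess at about 0.7 points at most for a 28-day gap. Protocol 12.3.1 also makes the test valid only if the primary endpoint succeeds. Both points limit the consequence.

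Finally, the exclusion works on completion of the form, whereas the proposed entry is the implant or refusal date. Any lag between the two leaves a small residue. None of this is a reason to keep the present origin.

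**Conclusion.** The concern holds and is minor. The plan's own rules create guaranteed survival time and count it as time at risk, which biases the hazard ratio whenever the arms differ in delay. At a gap of up to 28 days the shift is at most about 3% in either direction, and type I error rises to about 5.7%. This assumes constant hazard, 25.7% three-year mortality and 430 vs 540 subjects; higher early mortality would enlarge it.

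Neither document caps the enrolment-to-implant interval. If the arms differed by 91 days, the ratio would be about 0.90 and type I error 11–13%, but nothing in the documents supports such a gap. The three-month tolerance for Holter testing in SAP 3.1.2 should be largely common to both arms, because testing precedes the implant question. No figure is offered for 1.0 subjects, since their mortality is not stated. The primary analysis starts at implant and is unaffected.

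**What to change.** For the 1.5 mortality analysis and its 1.0 counterpart:

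1. Keep the groups, the exclusions and the censoring at late implant. Let each subject enter the risk set at the implant date or refusal date, through an entry time in PHREG on the enrolment time scale.
2. Do not use the decision date that appears in the exclusion "Patients with consent date after implant decision date" as entry for implanted subjects. Deaths between decision and implant would still be removed.
3. Use an entry time in the Cox model rather than a reset of time 0, because a reset leaves bias if mortality falls over time.
4. Start the group Kaplan-Meier curves at the implant or refusal date and label them so.
5. Report enrolment-to-record time by arm, with deaths and exits before the record by arm where known.
6. In the imputation model, use the cumulative hazard accrued after entry.
7. Do not substitute a fixed-group analysis that counts pre-implant deaths as non-implanted. A model with time-dependent implant status, entry at the 1.5 assessment and late-implant follow-up kept may serve as a sensitivity analysis.

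The cost is a few lines in the SAP and one model term, plus small changes to the curves and the imputation. The implant date is collected (Protocol 6.9.2). Visits are scheduled from implant or refusal (Protocol 6.10), so a refusal date should exist, but confirm that it is on the form. Precision is unchanged because the SAP already removes the early deaths. The estimate then applies explicitly to subjects who survive to the record, and a few early deaths stay outside the comparison.

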3.3.1 Power

This objective is not powered and the likelihood of a statistically significant test is not known. Therefore, it should not be a surprise if the endpoint is not statistically significant.

The following table shows what the power of the endpoint would be under various scenarios if doing a log-rank test (see PASS screen shot in the appendix for details). It is not known what effect adding covariates in a Cox proportional hazards model will have on the power.

[figure not shown]
In a retrospective analysis of SCD-HeFT, 1.5 prevention subjects without an ICD had a 25.7% mortality rate at 3 years compared to 18.5% for 1.5 subjects with an ICD. Under the sample size assumptions, it is expected that approximately 430 1.5 subjects will be implanted and 540 will not.

Power for 1.5 Prevention Mortality Endpoint

1.5 implanted sample size	1.5 not implanted sample size	Assumed 3-year Mortality				
		26% no ICD	26% no ICD	26% no ICD	22% no ICD	30% no ICD
450	550	88%	63%	32%	93%	82%
350	650	85%	60%	30%	91%	79%
360	440	80%	53%	27%	87%	73%
350	350	74%	48%	24%	83%	67%

3.3.2 Determination of Patients/Data for Analysis

All subjects in the 1.5 prevention cohort at the time of enrollment who do not meet the criteria in section 3.1.2 of this document will be included. The same criteria apply for the 1.0 subjects in their mortality analysis.

Hypothesis

Although this is an exploratory objective and is not powered, a hypothesis test will be done and compared to an alpha level of 0.05.

H_0 : Hazard ratio of patients with Chagas disease to patients without Chagas disease = 1
 H_a : Hazard ratio of patients with Chagas disease to patients without Chagas disease \neq 1

Only subjects with implant (regardless the prevention criteria group) will be included in the analysis. Subjects with missing information regarding Chagas disease will not be included.

The hypothesis will be tested separately for 1.0, 1.5, and secondary groups.

Analysis Methods

A Cox proportional hazard model will be used to compare the hazard rates of first appropriate VT/VF therapy between subjects with Chagas disease and subjects without Chagas disease within each group (1.0, 1.5, and secondary). The Cox proportional hazards model will only include the Chagas disease indicator. The null hypothesis will be rejected if the p-value for the Chagas disease indicator covariate is less than 0.05.

The analysis will be performed using SAS code similar to:

```
proc phreg data=alldataneeded ;
  class chagas;
  model firstVTVFappropTreat*event(0) = chagas;
run;
```

Time to Event Considerations

- Time 0 is the implant date and, if no events occur, subjects will be censored on the date of their latest device interrogation. Only spontaneous, appropriately treated VT/VF episodes as adjudicated by the episode review committee will count toward the endpoint.
- VT/VF episodes that cannot be adjudicated (due to not saving full episode data or any other reason) will be ignored. Often, these episodes are followed by episodes that can be adjudicated, and since the endpoint is time to first episode, effects on the results from these events will be minimal. In addition, these should be balanced between the comparison groups.

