5 APPENDIX

Sample size details

The % in each study group was based on estimates from the steering committee. It was assumed 1/3 would be enrolled in India, 1/3 in China, and 1/3 in the rest of the world. The table below shows the estimates from steering committee members, and the overall estimate, which was derived in a non-formalistic way from the physicians' estimates.

Physician	%Secondary		% Implanted					
			Secondary		1.5		1.0	
	My center	Others in my country	My center	Other centers in my country	My center	Other centers in my country	My center	Other centers in my country
[name] (Belarus)	75	No ans.	98	90	65	65	40	40
[name] (India)	70	80	80	10-80	No answer		15	15
[name] (China)	50	50	50	15	60	25	40	10
[name] (China)	30	55	50	30	40	30	30	30
Overall estimate	60*		57		45		22	

* Takes into account efforts to promote enrolling primary prevention subjects.

[figure not shown]
The program sim.sas produced power calculations based on the sample size assumptions. The program was run feeding in sample sizes from 4000-5000. Each study sample size was simulated 10,000 times, and the resulting power (% of time the lower one-sided 95% confidence limit of the hazard ratio (HR) was above 0.70) and the average hazard ratio for the 10,000 simulations are shown.

Sample size	Power	HR
4000	73.6	0.904
4050	74.9	0.904
4100	75.2	0.904
4150	74.6	0.903
4200	76.0	0.905
4250	75.6	0.904
4300	77.6	0.905
4350	76.7	0.903
4400	77.7	0.904
4450	78.1	0.903
4500	78.2	0.903
4550	79.2	0.904
4600	79.0	0.904
4650	79.5	0.905
4700	79.9	0.903
4750	80.5	0.903
4800	80.4	0.903
4850	80.6	0.902
4900	81.6	0.904
4950	81.8	0.904
5000	82.3	0.903

HR is included because those further away from 0.91 are under-estimating power.

4800 was chosen because the 4750 estimate of 80.5 may be too high (compared to 4700 and 4800).

Here is a screen shot of PASS mortality calculations

PROGRAM SIM.SAS

```
*****  
*****  
Program Name: SIM.SAS  
  
Study: IMPROVE SCA  
  
Purpose: Determining study sample size  
  
Inputs: None  
  
Outputs: None  
  
Cautions: None  
  
Revision  
History: Version Date Author Description  
----- ----- ----- -----  
-----  
1 09DEC13 [name] Initial  
Version  
*****  
*****/
```

```
OPTIONS PS=56;
```

```
/*  
SS: TOTAL SAMPLE SIZE OF STUDY  
PROBSEC: PROBABILITY OF SECONDARY (AS OPPOSED TO PRIMARY) PREVENTION  
PROB15: PROBABILITY OF BEING 1.5 GIVEN THEY ARE PRIMARY  
IMPSEC: PROBABILITY THAT A SECONDARY PREVENTION PATIENT GETS AN IMPLANT  

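### The exploratory Chagas analysis has no country term or stratification, so a geographic difference in therapy rates may be attributed to Chagas disease

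*SAP*

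**What the plan says.** Protocol 1.1 and SAP 2 list Chagas disease among the additional objectives. The SAP's analysis stands after 3.3.2; its own heading and introduction are not visible.

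- Population: "Only subjects with implant (regardless the prevention criteria group) will be included in the analysis". Subjects with unknown Chagas status are left out.
- Structure: "The hypothesis will be tested separately for 1.0, 1.5, and secondary groups".
- Model: "The Cox proportional hazards model will only include the Chagas disease indicator". The sample code agrees, with the single statement "model firstVTVFappropTreat*event(0) = chagas" and no STRATA line.
- Status and decision rule: "Although this is an exploratory objective and is not powered, a hypothesis test will be done and compared to an alpha level of 0.05". Then: "The null hypothesis will be rejected if the p-value for the Chagas disease indicator covariate is less than 0.05". The alternative is two-sided, and there is no multiplicity adjustment.

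On geography, Protocol 1.2 names ASEAN, Central and Eastern Europe, Greater China, India, Latin America, Middle East and Africa, and South Korea. The SAP Appendix adds: "It was assumed 1/3 would be enrolled in India, 1/3 in China, and 1/3 in the rest of the world". Neither document says where Chagas status is recorded or where cases are expected.

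**The concern.** A one-term Cox model compares Chagas subjects with all other subjects in the group whose status is known. If cases come mainly from a few countries, the indicator partly becomes a country label, and anything that makes device therapy more or less frequent there enters the hazard ratio.

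The planners did expect implanted populations to differ by geography. The comments in the SAP's simulation program put implant uptake among secondary prevention patients at 30% in China, 50% in India and 91% elsewhere. Only implanted subjects enter this analysis, so selection into it probably varies by place.

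The plan's reasoning about country does not settle the matter. SAP 3.3 drops country from the mortality model mainly because mortality may not differ much between countries, which says nothing about device therapy. Its second reason, small numbers in some countries, argues against estimating many country coefficients. Stratification estimates none.

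At stake is how a nominally significant Chagas result would be read. No primary or secondary conclusion depends on it.

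**Working it through.** **1. Calibration.** The Chagas analysis gives no sample size, event count or power to reproduce, so the study's own simulation was checked first. Re-coding it with the stated inputs (4800 enrolled, 22.5% first-year and 11.1% later annual event rates, 10% attrition, 2.24 years of accrual plus 2 years) gives 80.1% power and a mean hazard ratio of 0.903. The SAP Appendix states 80.4% and 0.903.

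Expected implants:
- Secondary: 4800 × 0.60 × 0.57 = 1641.6 (SAP: about 1650)
- 1.5: 4800 × 0.40 × 0.50 × 0.45 = 432 (SAP: about 430)
- 1.0: 4800 × 0.40 × 0.50 × 0.22 = 211.2 (SAP: about 200)

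The same inputs, with the program's hazard ratios of 0.91 (1.5 to secondary) and 0.68 (1.0 to 1.5), give about 530, 130 and 44 first events in the three groups.

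**2. Assumptions not in the documents.** Chagas cases occur in one region only. Prevalence there is p = 30%. The region supplies a share s of implants, from 10% to 33%. The true Chagas hazard ratio is 1. The regional hazard ratio r is varied.

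**3. Expected bias.** The fraction of non-Chagas comparators from the same region is f = s(1 − p)/(1 − sp). The apparent Chagas hazard ratio is roughly r/[1 + f(r − 1)].

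- s = 10%: f = 0.07/0.97 = 0.072. At r = 1.25, 1.25/1.018 = 1.23; at r = 1.5, 1.5/1.036 = 1.45.
- s = 33%: f = 0.231/0.901 = 0.256. At r = 1.25, 1.25/1.064 = 1.17; at r = 1.5, 1.5/1.128 = 1.33.

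The simulated medians, 1.17-1.22 at r = 1.25 and 1.34-1.45 at r = 1.5, agree.

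**4. Rejection of a true null at 0.05, two-sided.** There were 1,500 runs per cell, so the simulation standard error is at most √(0.25/1500) = 1.3 percentage points. Ranges run over s = 10% to 33%.

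| Group | r = 1.0 | r = 1.25 | r = 1.5 | r = 2.0 | Stratified by region, all r |
|---|---|---|---|---|---|
| Secondary (n = 1650) | 4-5% | 16-24% | 42-66% | 84-98% | 4-6% |
| 1.5 (n = 430) | 4-5% | 8-11% | 17-24% | 38-55% | 3-6% |

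The 1.0 group is not tabulated. At s = 10% it would hold about 200 × 0.10 × 0.30 = 6 Chagas subjects, and at r = 1.0 only 1,052 of 1,500 fits could be estimated.

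**5. Multiplicity, a separate matter.** Three independent tests at 0.05 carry a 1 − 0.95³ = 14.3% chance of at least one false rejection, with or without geographic confounding.

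**The case against.** The strongest reply is that the premise is not in the documents. They do not say that Chagas cases cluster, what share Latin America or any other likely source region supplies, or that therapy rates differ by region. With equal regional hazards the test holds its level. This stands, and is why the point is conditional.

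Some country differences are also limited by design: a Class I indication, Medtronic devices only, required programming and one Episode Review Committee. These narrow the routes for confounding. They do not remove differences in who accepts an implant.

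Four stronger readings are tempting but not supported.

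- A reader might infer that Chagas subjects are compared with non-Chagas subjects from every country. The objective's introduction is not visible and nearby text is redacted, so a restriction may exist there. If status was collected only in some countries, the missing-status rule would remove the rest.
- A reader might infer a larger bias from a simple two-group calculation. With, say, 40 Chagas and 520 other events, the standard error is √(1/40 + 1/520) = 0.164, and false rejection is 20%, 36% or 70% at regional ratios of 1.2, 1.3 or 1.5. That is an upper bound for a group the size of the secondary one. It assumes no comparator shares the region, in which case stratification would have nothing to compare.
- A reader might infer that the three tests cause or worsen the confounding. They do not. They are separate hypotheses in an analysis declared exploratory and unpowered.
- A reader might infer from the sample code, which has no BY or WHERE line, that the groups will be pooled. The text specifies comparison within each group and offers the code only as similar to what will be run.

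**Conclusion.** The point holds conditionally. As far as the visible text shows, the Chagas analysis has no protection against geographic confounding. A geographic difference may be attributed to Chagas disease if two things are both true: cases cluster by country, and appropriate-therapy rates differ between those countries and the others.

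Under the assumptions above, a modest regional hazard ratio of 1.25 raises the secondary-group error rate from 5% to about 16-24%. The 1.5 group, with about a quarter of the events, is less affected (8-11%), and no figure is relied on for the 1.0 group. Regional share, prevalence and regional hazard ratio are all assumed, so these results show sensitivity and do not forecast the trial.

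This is a low-cost improvement to an exploratory analysis. It does not threaten the trial's main conclusions.

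**What to change.** Keep the three within-group analyses. Add `strata country;` to the Chagas PROC PHREG step, with a broader region in place of country where numbers are sparse, and define that grouping before the data are analysed. Adding `by group;` would bring the sample code into line with the text.

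Restricting the analysis to countries with Chagas cases is an alternative, but it leaves differences among those countries uncontrolled unless strata are also used. If a geographic restriction already exists in text that is not visible, a cross-reference in the methods paragraph is enough for that part.

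Label the three p-values nominal and report each hazard ratio with its confidence interval. A single pooled test stratified by group and country would gain events, but it assumes a common hazard ratio and replaces three prespecified hypotheses, so it is optional.

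The cost is a line or two of code and a sentence in the SAP. Strata without Chagas cases drop out of the partial likelihood, so intervals widen, and the 1.0 group may have to be reported descriptively. Stratification removes between-country differences only; confounding within a country remains.
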